Home link:
Post hospital care to reduce HIV mortality in South Africa

Short title: Home Link

Protocol version: 6.0 dated 03 August 2022

Funder: National Institute of Mental Health, USA (Grant #1R34MH118998)

Implementing Partner: PHRU, South Africa

Principal Investigators: [name]

South African Principal Investigator: [name]

NCT04436289

Statement of Compliance

The study will be carried out in accordance with the design and specific provisions of this Human subjects ethics-approved protocol, with the ethical principles that are consistent with Good Clinical Practice (GCP) and the applicable regulatory requirements by the following:

- Declaration of Helsinki
- ICH GCP E6
- Completion of Human Subjects Protection Training

The Principal Investigator will assure that no deviation from, or changes to, the protocol will take place without prior agreement from the sponsor and documented approval from the Human Research Ethics Committee, except where necessary to eliminate an immediate hazard(s) to the trial participants. The Principal Investigator will promptly report to Human Research Ethics Committee any changes in research activity and all unanticipated problems involving risk to human subjects or others.

STUDY SUMMARY

Background: This is a pilot randomized clinical trial (RCT) to demonstrate the feasibility and acceptability of a structural and behavioral intervention to reduce mortality following hospital discharge for people with HIV (PWH) in South Africa. Our prior study showed that among 121 PWH discharged, 54% were readmitted and 26% had died by six months following discharge. In the prior study, we identified that missing clinic visits after discharge was associated with death. Here we are seeking to overcome key barriers in piloting a home-based post-hospital care intervention. Our approach is informed by a conceptual model of key barriers to the care transition along with a behavioral explanatory model, the Behavioral Model for Vulnerable Populations.

The overarching goal of this study is to tailor and pilot the intervention that shifts initial post-discharge care from the out-patient clinic to the home and provides patient-centered counseling (Home Link intervention). For the intervention to prove effective it will need to substantially reduce post-discharge mortality. Specifically, in the Home Link intervention, a team will conduct home visits to (1) provide a structured clinical assessment; (2) reconcile medications, (3) provide psychosocial support through patient-centered counseling, and (4) assess home needs (food security). These visits will start one week after discharge and be repeated every two weeks until the participant is stabilized and ready to initiate lower intensity clinic-based services or three months have elapsed.

Aims: The aims of the study are to pilot a randomized clinical trial of home delivery of health services during the post-hospital period for PWH.

Methods: This project is a pilot randomized clinical trial (RCT) to refine and test the feasibility, acceptability, and preliminary effectiveness of the HomeLink intervention. At the conclusion of the R34 grant period we will have a protocol and procedural manual ready for a full RCT powered for effectiveness.

Significance: The proposed study is consistent with NIH HIV/AIDS highest priority research and the South African National Strategic Plan on HIV, TB, and STIs 2017-2022. The research addresses the HIV/AIDS Research Priority of “retention and engagement in these services, and achievement and maintenance of optimal prevention and treatment responses.”

Key Personnel

Name	Responsibility	Contact
PHRU		
[name] Site Principal investigator	Project management, stakeholder engagement, dissemination and manuscript preparation.	[contact] Email: [contact]
[name] Co-Investigator	Project management and clinical oversight	[contact] Email: [contact]
JOHNS HOPKINS UNIVERSITY		
[name] Principal Investigator	Developing procedures, protocol, project management, stakeholder engagement, dissemination and manuscript preparation.	[contact] [contact] Email: [contact]
[name] Co-Investigator	Responsible for contribution to design and analysis of RCT components.	Phone: +1 Email: [contact]
[name] Research Manager	Study design, protocol writing, study management, study implementation and oversight.	[contact] Email: [contact]

Contents

Statement of Compliance.....	2
1 INTRODUCTION.....	8

1 INTRODUCTION

1.1 Background

A.3. Sub-Saharan Africa HIV mortality

In 2016 in South Africa approximately 154,000 PWH died.¹ Of these deaths, 110,000 have been characterized as excess mortality due to HIV (HIV associated deaths).^{2,3} Overall, HIV-associated deaths are associated advanced disease defined by a low CD4 count.⁴⁻⁶

A.4. In-Hospital and Post-Hospital Mortality in Africa

Inpatient mortality among people with HIV (PWH) in Africa is uniformly high ranging from 17.2 to 29.6% across the continent, including in South Africa.⁴⁻⁶ Following discharge from an index hospitalization the mortality is also high. In our preliminary work we have observed a 26% mortality in the 6 months after hospital discharge. This observation is consistent with mortality from other reports: 50% mortality at twelve months and 30% and 31% at six months reported from Tanzania, Kenya, and South Africa, respectively^{7,8}

A.5. The contribution of Post-Hospital Mortality to Overall Death among People with HIV

In South Africa there are approximately 84,633 public sector acute care hospital beds of which approximately 25% are adult medicine beds.⁹ By extrapolating the post-discharge mortality we observed to all discharges among PWH in South Africa we can estimate the annual mortality among PWH with a hospital discharge in the past six months. Considering the national proportion of all admissions that are for PWH, the average length of stay, and the annual readmission rate an estimated 240,000 PWH are admitted to medicine wards in South Africa annually.^{10,11,12,13} A six-month post-hospital mortality of 26% suggests a total of 62,374 post-hospital deaths among PWH. This number of deaths represents 40% of the approximately 154,000 total annual deaths among PWH in South Africa.^{1,2} A modest reduction in post-hospital deaths could substantially reduce overall HIV mortality in South Africa.

A.6. Causes of Post-Hospital Death

Some post-hospital deaths may be unavoidable due to advanced or incurable disease. Other post-hospital deaths may be avoidable with improved retention in care. A study from Johannesburg, South Africa assessed loss from care for HIV-TB co-infected patients; only 42% of patients discharged were known to have been to an HIV clinic within 30 days of hospital discharge (the time needed to obtain or refill ART prescriptions at the time of the study)¹⁴ Similarly in our preliminary study, only 19% of participants attended a scheduled follow-up visit. Failure to attend a scheduled visit was associated with subsequent mortality in our preliminary study and in a report from Tanzania.⁷ At present, there is limited research regarding approaches to retaining PWH in care during the post-hospital transition.^{4,15,16}

A.7. The Hospital Admission and Re-admission Cost to the Medical System

In addition to the human toll of post-hospital mortality, there is a substantial cost to the health care system. The estimated average cost per medical admission in South Africa is USD1426 (USD364 per day).¹⁷ Reducing the frequency of readmission and death (often during readmission) has the potential to reduce health system costs. Among the 121 PWH we observed in our preliminary study, 49 were readmitted once, 13 twice, and 2 three times within six months of discharge for an estimated hospital cost of USD115,506. Improving outpatient engagement in care may reduce this cost.

A.11. Factors Associated with Accessing HIV Care in Africa

Although little has been described regarding engagement in care following hospitalization in southern Africa, a great deal is known about failure to link to care. Study team members and other investigators in the field have identified factors associated with linkage to care and continued engagement in care on multiple socio-ecological levels.^{18,19} On an individual level feeling healthy, not accepting an HIV diagnosis or allopathic care, internalized or anticipated stigma, fear, and food insecurity either diminish the perceived value of care or increase the perceived costs.¹⁹⁻²² Personal resilience and coping skills can reduce some of these potential costs while understanding or recognizing the role of ART can increase perceptions of value. On an interpersonal level, social support, acceptance, and encouragement of health seeking behaviors can contribute to care engagement. Clinic-level costs including travel, need for repeat visits, long wait times, needing to arrive very early in the morning, enacted stigma, inadvertent disclosure by attending a clinic, and demeaning behavior from health staff are barriers to care engagement.²³⁻²⁷ Supportive health care workers can improve engagement. Strengths-based counseling and eliminating structural barriers have had demonstrated success in increasing linkage to care.²⁸⁻³³ Furthermore, little is known about what impact, if any, COVID-19 has had on patient engagement in care following hospitalization.

A.8. Hospital Transition Programs in High Income Countries.

In the absence of hospital transition intervention studies from sub-Saharan Africa, studies from high income countries may provide useful lessons. Best practice guidelines regarding hospital discharge are largely focused on educating the patient and household members, medication reconciliation and pharmacy-based interventions, and communication between the discharging hospital and ambulatory care providers. Additional recommended or tested strategies include personal contact via telephone calls, home visits, or scheduled clinic visits shortly after hospital discharge.³⁴ Several studies have evaluated home medical visits following discharge. A recent meta-analysis of 47 randomized trials reported reduced readmission in five studies; 4 of these included home medical visits.^{35,36} Post-hospital interventions that included home visits compared to those that did not were more likely to improve outcomes.

A.9. Home-Based ART Initiation or Maintenance in Africa

Home-based ART has been studied in sub-Saharan Africa to increase ART initiation, improve retention, or do both. A study in Uganda randomized participants to care at home or at the health facility starting at the first visit after ART initiation. Viral load suppression and mortality, to 24 months, was similar by study arm.^{37,38} Studies of home ART initiation in Malawi and Lesotho reported higher ART initiation and improved or similar retention in care with household ART initiation followed by subsequent facility-based care when compared to standard facility-based ART initiation.^{29,30} These studies suggest the acceptability, feasibility, and potential for better outcomes with home-care based interventions.

A.10. Public Health Sector Home Visit Model in South Africa

The National Department of Health, South Africa, began a process known as Primary Care Reengineering in 2010. An integral component of this initiative is community and household care. Specifically, each of the >5000 primary care clinics and community health centers will have a “ward-based outreach team” or WBOT. The teams are designed to be led by a primary care nurse and include enrolled nurses and lower level cadres including counselors. The primary mandate of the WBOTs is to improve health outcomes of South Africans through provision of

home and community-based health services.³⁹ At present, there is no defined approach for post-hospital follow-up nor is there a structured system of communication between the discharging hospital and clinics or WBOT teams.⁴⁰ The proposed intervention fits within the current initiative of the South African Department of Health and has the potential to provide valuable new knowledge to guide WBOT deployment.

1.2 Study objectives

The overarching goal of this proposal is to demonstrate clinical trial feasibility, acceptability, and preliminary efficacy of structured post-discharge medical home visits to reduce mortality following the transition from the hospital to home. We are proposing a pilot randomized clinical trial (RCT) to determine preliminary efficacy, feasibility of trial implementation and intervention delivery, acceptability of the intervention, the effect of the intervention on barriers to care, and to obtain detailed baseline psychosocial and medical needs to inform intervention refinement and explain outcomes (Figure 1).

The primary objectives of this study are:

1. To estimate 6 month mortality rates and assess for evidence of efficacy of the Home Link intervention compared to care as usual.
2. To determine the feasibility, acceptability, and effect of the Home Link intervention on identified barriers to care.
3. To characterize medical and behavioral needs among participants in the study.

The secondary objectives of this study are:

1. Determine post-hospital health care out-of-pocket costs for participants
2. Assess re-admission
3. Estimate 12 month mortality by study arm
4. To understand experiences around the time of the passing of the participant from the family members perspective

1.3 Significance

This study fits with the South African National Strategic Plan to increase effective HIV treatment. The study is also consistent with NIH HIV/AIDS highest priority research and the South African National Strategic Plan on HIV, TB, and STIs 2017-2022. Given the high post-discharge mortality findings from this study could contribute to approaches to reduce mortality for PWH.

2 METHODS

2.1 Study design

This is a pilot randomized clinical trial (RCT) to refine and test the feasibility, acceptability, and preliminary effectiveness of Home Link.

2.2 Study setting

This pilot operational research study will be conducted in Matlosana. All participants will be recruited from Tshepong Hospital. Eligibility will include residing within Matlosana sub-district.

2.2.1 Tshepong Hospital

Tshepong Hospital is a tertiary care hospital in Matlosana. An average of 30 patients are admitted to medicine wards daily. Nearly 50% are PWH.

2.2.2 Description of the geographical areas of study implementation

The proposed study will be conducted at the 500 bed Tshepong Hospital in the Northwest Province. Tshepong Hospital is one of 5 hospitals in Kenneth Kaunda District and the single tertiary care public hospital serving the population of 400,000 in Matlosana (Figure 1). This hospital was selected due to its size, heterogeneous catchment area (rural to urban), and long-standing working relationships with the research team. Tshepong Hospital currently provides discharge services that include (1) discharge counseling and education provided by counselors and (2) a medical record notebook with a discharge summary for the patient to take to his or her clinic visits.

[figure not shown]
2.2.3 Rationale for selecting geographical areas of study implementation

We selected Tshepong Hospital based on a long-standing working relationship between the PI, PHRU, and the Tshepong Hospital. This has included a prior study of post-hospital outcomes

2.3 Study Population

The population is comprised of adults (≥ 18 years old), either male or female, spending at least two nights in a medical ward of Tshepong Hospital. We will only include individuals with known HIV status, either HIV-positive or HIV-negative. We propose to recruit up to 180 HIV-positive and 60 HIV-uninfected participants.

Randomization to the intervention vs control arms will be stratified by HIV status.

2.3.1 Inclusion criteria

- Tested for HIV (can be living with HIV or HIV-uninfected) – HIV negative participants should have a documented test from within the previous 3 months
- Residing within Matlosana sub-district
- Agree to post-discharge follow-up including home visit
- Able to provide informed consent or, if lacking capacity at the time of recruitment (if unable to answer basic orientation questions including name, month/year, and residence location), as determined by the study team, having a next of kin able to provide informed consent

2.3.2 Exclusion criteria

- <18 years of age
- Length of stay <2 nights
- Unknown HIV status at the point of study screening and enrollment
- Failure by the patient or next of kin to provide informed consent to be followed up by study staff after discharge
- Residing outside of Matlosana sub-district
- Not speaking any of the languages spoken by the study team

Late exclusions occurring after enrolment

- Death prior to hospital discharge
- Discharged too late for the study team to deliver the intervention
- Transfer to another hospital
- Relocation outside of Matlosana sub-district at the point of discharge or within 7 days of discharge

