2.4.2 Randomization

The total sample size is 180 HIV-positive and 60 HIV-uninfected adults. There will be a total of four study arms comprising of two arms for HIV uninfected and two arms for PWH. We will

perform individual randomization blocked by HIV-status to enroll 30 HIV-uninfected adults per arm and 90 PWH per arm (Figure 2).

[figure not shown]

Figure 2: Randomization Study Arms for Home Link Intervention

1. Randomization of hospital patients for recruitment: On each participant recruiting day, a list of all medical ward patients will be generated, and each patient will then be randomly listed in order of planned recruitment. Patients will be approached at any time after admission if they are next on the list for recruitment until the enrolment target is reached for that day. A new list will be generated each day including only those patients admitted 2 days prior (or on Thursday, Friday and Saturday on Mondays).
2. Randomization to study arm: After informed consent and completion of baseline CRFs the participant will be randomized to care as usual or Home Link arm.

Randomization will be conducted immediately after eligibility criteria for the participant has been documented and informed consent has been signed. Participants will be randomized 1:1 to either the care as usual or the Home Link intervention arms using computer-generated random numbers, stratified by HIV-status.

A study staff member will SMS a dedicated study telephone number – staffed by someone not linked to any other aspect of the conduct of the study. Details of the eligible participant, including randomization group (1=living with HIV; 2=living without HIV), initials (first two letters of the first name and first two letters of the surname), age, and sex, will be sent via SMS to the randomizing team. A member of the randomizing team will then relay the allocation details (within 15 minutes) to the study staff member

who requested the randomization via SMS. Proof of randomization will be sent to the study staff member who will place the proof into the participants' study file.

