2.6 Verification of hospital discharge date

Study staff will determine when study participants are discharged from the hospital in order to plan and schedule data collection follow-up to ascertain outcomes and to schedule the Home Link intervention home visits (for those in the Home Link arm).

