2.7 Post-discharge follow-up

The primary outcome is mortality six months after hospital discharge. Secondary outcomes include mortality 12 months after hospital discharge, number of nights spent in a hospital,

number of ambulatory clinical encounters after the index hospitalization, and patient out-of-pocket costs for medical care. Outcomes will be assessed through scheduled contact and completion of a structured questionnaire with the participant or designated next of kin (either telephonic or in person if telephonic fails) at 8, 12, 26, and 52 weeks. Mortality will be further ascertained through a 26 and 52 week review of the Tshepong Hospital file (including the affiliated Klerksdorp hospital files) and matching of participant national identification numbers to the vital statistics register through consultation with the Department of Home Affairs. Repeat hospitalization will be ascertained using self-report / next of kin report and hospital records. Most subsequent hospitalizations can be expected to be at Tshepong Hospital due to the substantial distance to reach the next nearest hospital (>50 km to a lower level facility). In our prior experience we have observed rare use of alternative hospitals. Clinic visit data will be ascertained by self-report followed by verification through review of clinic paper or electronic (tier.net) records and National Health Laboratory Service electronic records (TrackCare).

Table 2. Scheduled visit windows

Visit name	Period	Primary goal
8 week follow-up	20 – 70 days	Maintain contact with participant
12 week follow-up	71-150 days	Assess care engagement, care satisfaction, mortality
26 week follow-up	151 – 245 days	Assess care engagement, , mortality; conduct psychosocial assessment
26 week hospital file review	>26 weeks post-hospital	Abstract care visits, re-admission, death
26 week Home Affairs vital status review	>26 weeks post-hospital	Match South African ID numbers
26 week care verification	>26 week post-hospital	Use electronic and paper files to verify self-reported clinic visits
52 week follow-up	365-455 days	Assess care engagement, mortality
52 week hospital file review	>365 days post-hospital	Abstract care visits, re-admission, death
52 week Home Affairs vital status review	>365 days post-hospital	Match South African ID numbers

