2.7.2 Mortality

Mortality will be ascertained via:

- (1) Telephonic contact with participant (alive) or next of kin, as provided by the participant, reporting a death
- (2) Review of the Tshepong Hospital paper file
- (3) South African Home Affairs vital statistics query using the participant national ID number

Mortality will be assessed after six months and again after twelve months.

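### Two post-randomisation exclusions depend on Home Link delivery or timing, with no equal-application rule and no named analysis set, so the six-month mortality comparison is open to differential exclusion

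*Combined protocol and SAP*

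**What the plan says.** **Timing of randomisation.** Section 2.4.2: "Randomization will be conducted immediately after eligibility criteria for the participant has been documented and informed consent has been signed". This takes place in hospital. On disclosure of the arm: "A member of the randomizing team will then relay the allocation details (within 15 minutes) to the study staff member".

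**Late exclusions.** Section 2.3.2 then lists four reasons for exclusion after enrolment. Two are death before discharge and transfer to another hospital. The other two are the subject here: "Discharged too late for the study team to deliver the intervention" and "Relocation outside of Matlosana sub-district at the point of discharge or within 7 days of discharge".

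**Contacts after discharge.** On Home Link visits, the Study Summary says: "These visits will start one week after discharge"; section 2.5.2 agrees. In Table 2 the first follow-up contact common to both arms is the 8-week contact, with a window of days 20 to 70. Section 2.6 covers discharge dates for everyone: "Study staff will determine when study participants are discharged from the hospital".

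**Outcome and analysis.** Section 2.7: "The primary outcome is mortality six months after hospital discharge". The first primary objective in section 1.2 includes looking for evidence of efficacy against care as usual. Tables 3 and 6 specify a chi-square test between arms. Neither says which participants enter it.

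**The concern.** Both exclusions act after randomisation, when study staff know the arm, and each leaves room for unequal use.

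- **Late discharge.** The criterion is framed by whether the team can deliver the intervention. A care-as-usual participant has nothing to be delivered, so staff must either judge a hypothetical or leave the rule unused in that arm. No date or interval defines too late.
- **Relocation within 7 days.** In that interval only Home Link has a visit coming due. A move is therefore easier to discover in Home Link than in care as usual, even if staff act in good faith.

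Patients who stay long in hospital, or who move away at discharge, may well differ in prognosis from the rest. If more of them leave one arm than the other, the groups compared are no longer those that were randomised. The direction of the resulting bias cannot be predicted.

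A second problem needs no assumed rate: because no analysis set is named, the denominators of the primary test are undefined.

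**Working it through.** **Inputs from the documents.** Control mortality 26%, alpha 0.05 and 90 people with HIV per arm (section 3.2, Table 9). The documents give neither the share excluded (x) nor the six-month mortality of the excluded (m), so both are assumptions.

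**Step 1: reproduce the plan's power.** With p1 = 0.26, p2 = 0.10, n = 90 and mean proportion 0.18:

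- s0 = √(2 × 0.18 × 0.82 / 90) = 0.0573
- s1 = √((0.26 × 0.74 + 0.10 × 0.90) / 90) = 0.0560
- power = Φ((0.16 − 1.96 × 0.0573) / 0.0560) = 0.803, as in Table 9.

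Ninety per arm is also the smallest number that gives 80% power by this formula, so there is no reserve for exclusions.

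**Step 2: bias with no true effect.** Both randomised arms have 26% mortality. After exclusion, an arm's observed mortality is (0.26 − x·m) / (1 − x). For example, with 10% of Home Link and 5% of care as usual excluded, dying at 50%:

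- Home Link: (0.26 − 0.05) / 0.90 = 23.33%
- care as usual: (0.26 − 0.025) / 0.95 = 24.74%
- difference: −1.40 points.

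The two-sided type I error comes from exact binomial enumeration of the uncorrected chi-square test, with 90, 86 or 81 per arm for 0%, 5% or 10% excluded.

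| Home Link excluded | Care as usual excluded | Mortality of excluded | Apparent difference (points) | Type I error |
|---|---|---|---|---|
| 0% | 0% | n/a | 0 | 5.0% |
| 10% | 5% | 40% | −0.8 | 5.2% |
| 10% | 5% | 50% | −1.4 | 5.5% |
| 10% | 5% | 60% | −2.0 | 5.9% |
| 5% | 0% | 40% | −0.7 | 5.2% |
| 10% | 0% | 60% | −3.8 | 8.6% |
| 10% | 0% | 10% | +1.8 | 6.1% |
| 5% | 10% | 50% | +1.4 | 5.5% |
| 10% | 10% | 50% | 0 | 5.0% |

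Negative values favour Home Link. The bias is also zero whenever m = 26%, that is, when exclusion is unrelated to prognosis.

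**Step 3: scale.** The standard error of the difference is √(2 × 0.26 × 0.74 / 90) = 0.065, or about 6.5 points.

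**Step 4: cost of keeping undelivered participants.** Assume they die at 26%.

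- 5% undelivered: Home Link mortality 0.95 × 0.10 + 0.05 × 0.26 = 0.108; power 75.3%.
- 10% undelivered: 0.90 × 0.10 + 0.10 × 0.26 = 0.116; power 69.9%.
- For comparison, excluding the same shares equally from both arms (86 or 81 per arm) leaves power of 78.5% or 76.0%.

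**The case against.** The strongest reply is that this is exposure to bias and not a demonstrated error. The list in section 2.3.2 names no arm, so its plain reading covers everyone. Too late could mean a calendar limit near the end of the study, which would fall on both arms alike and create no bias. Relocation at the point of discharge can be captured in both arms, because the discharge form (D001) covers both. The locator update and follow-up forms (L002, F001) also cover both and could reveal an early move in retrospect. The assumed shifts are small, section 3.2 ranks feasibility and acceptability first, and section 5.5 sets no stopping rule for effectiveness.

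Most of this is fair and limits the size of the point. It does not remove it. No calendar date and no equal-application rule is written. The discharge form settles relocation at discharge only; it does not settle moves in the following 7 days or the judgement about deliverability. Mortality is still the named primary outcome, and section 2.7.4 reads the feasibility and acceptability results alongside the efficacy results.

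Two further objections concern the remedy. First, the bias figures and the dilution figures assume different mortality in the affected group, so they cannot be traded off directly. That is correct. A dated limit applied equally to both arms would cost less power. Second, transfer is also post-randomisation and may be prognostic, yet the fix below keeps it as an exclusion. The reason is that transfer before discharge can be read from the hospital record without judging whether a visit was deliverable. It should still be reported by arm.

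**Conclusion.** The concern holds and should be fixed, though it is not a fatal flaw. The protocol states a post-randomisation exclusion tied to delivery of one arm's intervention and a second whose window closes before care as usual has a scheduled follow-up contact. It does not require equal application and does not define the primary analysis set.

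Under the assumed unequal exclusions in both arms, the shift is 0.8 to 2.0 points if more of Home Link is excluded, with type I error of 5.2% to 5.9%. The most extreme case shown is 3.8 points and 8.6%. The sign can reverse. All of these rest on assumed exclusion rates and mortality. Against a standard error of about 6.5 points the effect is small in a pilot of this size. The undefined denominator rests on no such assumption.

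**What to change.** **Section 2.8.** Define the primary mortality set as all randomised participants discharged alive from the index Tshepong admission, analysed in the assigned arm. This fits an outcome counted from discharge.

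**Section 2.3.2.**
- Treat late discharge and relocation (at discharge or within 7 days) as recorded reasons for non-delivery, not as exclusions. Continue to seek vital status by the routes in section 2.7.2, which begin with "Telephonic contact with participant (alive) or next of kin, as provided by the participant, reporting a death" and add the hospital file and the Home Affairs match.
- Keep only in-hospital death and transfer before discharge as exclusions, and state that they apply identically in both arms. Say that transferred patients fall outside the discharged-alive set.
- If a calendar limit on discharge is intended, give it as a date that applies to both arms and build it into the set.

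**Reporting.** Show all late events by arm and reason.

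**Cost.** A few sentences, and a few more follow-ups through routes already planned. The real price is dilution: power of 75.3% or 69.9% in place of 80.3% if 5% or 10% of Home Link is undelivered, on the assumption in Step 4. A supplementary analysis that applies one dated limit to both arms can be shown alongside.
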